#### **5.5.1 Early Termination Study Visit**

N/A

## **6 STUDY EVALUATIONS AND MEASUREMENTS**

**Study 1:** A qualitative interview guide will be sent for review to IRB before the qualitative interviews are administered. The interviews will explore: (1) tobacco cessation treatment needs, (2) barriers to treatment engagement, (3) barriers to treatment delivery, (3) the treatment protocol, (4) the training protocols, (5) recruitment strategies, and (6) the measurement protocol.

**Study 2 & 3:** A qualitative guide will be sent for review to IRB before the qualitative interviews are administered.

## Patient Assessments.

Demographics We will assess patient demographics including gender, race/ethnicity, and age.

Tobacco use history. We will assess tobacco use history including number of cigarettes per day, years of smoking, use of other nicotine/tobacco products, prior use of tobacco cessation treatments (counseling and medication).

Fagerstrom test for Nicotine Dependence. the Fagerstrom Test for Nicotine Dependence is a 6-item measure of tobacco dependence.

The Biener Contemplation Ladder is a single item measure of readiness to quit smoking.

Use of tobacco cessation treatment. Patients will be asked if they have participated in tobacco cessation counseling of any kind (in-person, telephone, or group counseling), or if they have received or used any of the 7 FDA-approved tobacco cessation medications.

Abstinence. Patients will be asked if they have smoked in the last 7 days, and the last 30 days, if they have made an at least 24 hour quit attempt since the last assessment, and the Biener contemplation ladder.

Client Satisfaction Questionnaire. The Client Satisfaction questionnaire is an 8-item measure of health program acceptability.

Expired Air Carbon Monoxide. Expired air carbon monoxide will be measured using a bedfont smokerlyzer.

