Subject Population Key Criteria for Inclusion and Exclusion:	Participants will be patients and employees (leadership and clinical staff) at two community mental health centers in Minnesota. Inclusion criteria for employees are to be on staff at the two community mental health center recruitment sites. There are no exclusion criteria for employees. Patient inclusion criteria include being English-speaking, current smokers (>25 days/month), patients at the community mental health center. Patient exclusion criteria includes judged by community mental health as being unable to participate in research (due to cognitive impairment or any other reason), no access to a telephone, no access to an address at which they can receive mail.
Number Of Subjects	Total Number of Subjects: Study 1: 29; Study 2: 25 patients, 33 staff; study 3: 50 patients, 200 staff Total Number at Hennepin Healthcare: 0 Total Number of Sites: 2
Study Duration	For study 1, each subject's participation will last one day, the entire study will last 3 months For study 2, each patient subject's participation will last 3 months, staff participation will last 6 months, the entire study will last 6 months For study 3, each patient subject's participation will last 15 months, staff participation will last 12 months, the entire study will last 18 months
Study Phases Screening Intervention Follow-Up	Study 1 potential participants will be approached for a single time point consent and qualitative interview. Study 2 potential patient participants will be approached in person or via an information letter, interested participants will complete informed consent and a baseline survey, all participants will receive and outreach attempt and may choose to enroll in counseling, participants will complete a follow-up survey 3 months post-enrollment. Some participants will be selected to participate in qualitative interviews. Study 3: potential participants will be approached, interested participants will complete informed consent and a baseline survey. 3 months later, participants will complete a second baseline survey. Participants will receive 3 outreach attempts, 3 months apart. At each outreach, participants will be given the choice of whether to enroll in counseling. Participants will complete follow-up surveys at 6, 9, and 15 months post enrollment.

---

---

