### Study 3: Full Length Pilot

Procedures		Enrollment/Baseline 1 (day 0-60)	Pre-implementation (day 60-90)	Baseline 2 (day 90-180)	Implementation (Day 120-300)	3-month follow-up (day 210-240)	6-month follow-up (day 300-330)	12-month follow-up (Day 390-420)
Organizational coaching	Online training		X					
	Readiness meeting		X					
	Coaching calls		X		X			
	In-person workshop		X					
	Sustainment meeting				X			
Staff training	Online training		X					
	In-person workshop/role play		X					
	Learning community		X		X			
	Performance Feedback				X			
Patient recruitment and enrollment	Identify smokers		X					
	Informed consent		X					
Intervention delivery	5 A's delivered at each visit				X			

Intervention delivery		Enrollment/Baseline 1 (day 0-60)	Pre-implementation (day 60-90)	Baseline 2 (day 90-180)	Implementation (Day 120-300)	3-month follow-up (day 210-240)	6-month follow-up (day 300-330)	12-month follow-up (Day 390-420)
	Proactive outreach counseling			X	X			
Assessment	Pre-post training evaluations	X						
	After visit surveys	X	X	X			X	
	Patient baseline surveys	X	X					
	Follow-up surveys				X	X	X	
	Biochemical verification						X	
	Stakeholder interviews						X	X

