### **4.2.3 Study procedures and visits study 3**

#### **Patients.**

Enrollment. Patients will provide written or electronic, informed consent. They will then complete a baseline survey. At the time of the provider training, they will complete a second baseline survey. Following the second baseline survey, the smoking cessation case manager will begin an outreach attempt (phone, text, or in person). During the outreach, they can elect to enroll in smoking cessation counseling and/or get help from the case manager to reach out to their providers to obtain smoking cessation medication. Outreach attempts will be repeated at 3 months, and 6 months following the second baseline survey.

Follow-up. Participants will complete additional follow-up surveys at 3, 6, and 12 months following the second baseline survey. Follow-up surveys will be completed by phone or via an online survey. Participants who report abstinence at the 12-month follow-up will be asked to complete a mailed or in-person CO test. 5-6 patients will participate in a qualitative interview.

Providers will receive a study fact sheet and baseline survey prior to the trainings. Completion of the baseline survey or attendance at the trainings or coaching calls will be considered consent to participate. Providers will complete a recorded, online training via Zoom or an in-person training regarding providing smoking cessation interventions to patients. This training will be attended by investigators from Brown University ([name], [name]) who will edit training videos for future site use. Providers will then have the opportunity to participate in coaching calls for 9 months. Providers will receive performance feedback about smoking cessation interventions from patient surveys or electronic health record data starting at the second baseline through 9 months post implementation. Leadership for the organizations have already agreed to participate. Leaders will participate in a virtual or in person site visit at the beginning of the study. 5-6 employees will participate in a qualitative interview. We will work with the site to create the following implementation tools: handouts about community smoking cessation resources, handouts about smoking cessation medications, decision aids to complete the 5 As, templated language to put in electronic health record notes.

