## 6.2 Efficacy Evaluations

Feasibility will be measured by the percent of providers who: attend the online and in person trainings, complete role plays, attend coaching calls, and receive performance feedback. We expect the majority (>75%) of providers and leaders to attend the trainings and receive performance feedback. For patients, feasibility will be measured by the proportion of patients who enroll in the study, the proportion who accept a proactive outreach and the proportion who complete the follow-up. Previous studies (preliminary studies 1-3) using this recruitment strategy have yielded a 30-44% response rate to the enrollment invitations, 62-71% for the proactive call, and 66-74% for follow-up assessment. Results in this range would be considered feasible.

Acceptability. Patients will complete the 8-item Client Satisfaction Questionnaire (CSQ) during the follow-up assessment. Qualitative interviews with 5-6 patients and 5-6 providers will be conducted at the 3-month follow-up (study 2), and 15 month follow-up (study 3). Interviews will be conducted by a trained research staff member. Interviews will contain open ended questions about treatment (for patients) and implementation (for providers and leaders) acceptability, burden, and suggestions for improvement.

Effectiveness. Implementation Effectiveness will be evaluated by the proportion of patients who receive the 5As and the proportion who report using smoking cessation counseling and medication measured 3-months after the start of the implementation period (study 2) and at 3, 6, and 12 months post baseline 2 (study 3) assessed via patient report. Patient Effectiveness will be measured by carbon monoxide (CO)-confirmed 7-day point-prevalence from tobacco post-intervention (3 months for study 2 and 12 months from second baseline for study 3). Secondary patient outcomes will include: 30-day point-prevalence abstinence, the number of self-reported ≥24 hour quit attempts and reductions in smoking via cigarettes per day.

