Acceptability will be assessed based on the 8 item Client Satisfaction Questionnaire (CSQ) during the follow-up assessment, as well as qualitative interviews at the 12-month follow-up. Interviews will contain open ended questions about treatment (for patients) and implementation (for providers and leaders) acceptability, burden, and suggestions for improvement. The treatment will be considered acceptable if  $\geq 80\%$  of participants respond that they are at least somewhat satisfied with their participation. Average acceptability scores will be reported. Initial effectiveness will be evaluated with respect to both implementation and patient outcomes. First, we will summarize CMHC-level implementation data with respect to treatment delivery and utilization (e.g., proportion of patients receiving each of the 5A's, using smoking cessation counseling and medication) and compare across centers. Next, baseline, 3-, 6-, and 12-month patient cessation outcomes (7-day PPA and number of quit attempts), will be summarized among the aggregate sample and by CMHC. We will explore the adjusted effects using a series of generalized linear mixed effects models adjusted for potential confounders, baseline values and clustering. Models allow for flexible distribution of the outcome (binary, count) and adjust standard errors for the clustered nature of the data (clustered by provider within CMHC). Models will include a random effect for CMHC and will further adjust for potential confounders (including variables that might differ between CMHC's). Similar models can be used to test the effects on secondary outcomes (e.g., cigarettes per day) during the post-implementation period (3-, 6- and 12-months) adjusting for baseline, and to explore the effect of implementation at the patient level (use of counseling and medication) and at the provider level (SSL dose) as a predictor of primary and secondary cessation outcomes.

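### On the text schedule, Study 3's quit-attempt item looks back 6 months at month 12 but 3 months at baseline 2, month 3 and month 6, so an unchanged rate would tend to look like a late rise

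*Combined protocol and SAP*

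**What the plan says.** **The item.** Section 6, Patient Assessments (Abstinence), asks patients "if they have made an at least 24 hour quit attempt since the last assessment". As worded this is a yes/no question whose look-back runs to the previous survey.

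**The outcome.** Section 6.2 treats it as a count: "Secondary patient outcomes will include: 30-day point-prevalence abstinence, the number of self-reported ≥24 hour quit attempts". Section 7 also speaks of a number: "baseline, 3-, 6-, and 12-month patient cessation outcomes (7-day PPA and number of quit attempts), will be summarized", in the aggregate sample and by center. It then plans to explore adjusted effects with "generalized linear mixed effects models adjusted for potential confounders, baseline values and clustering", for binary or count outcomes. No rate, time-at-risk term or common look-back is given, and the baseline survey meant is not named.

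**The schedule in the text.** The Synopsis places baseline 2 three months after enrollment and adds "Participants will complete follow-up surveys at 6, 9, and 15 months post enrollment". Section 4.2.3 agrees: "Participants will complete additional follow-up surveys at 3, 6, and 12 months following the second baseline survey". It also says: "Outreach attempts will be repeated at 3 months, and 6 months following the second baseline survey". Section 7.1 sets the Study 3 primary time point at 12 months post-implementation, and section 9.7.2 pays for five assessments.

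**The schedule in the table.** The Study 3: Full Length Pilot table begins its month-6 column heading "6-month follow-up (day 300-330" and puts month 12 at days 390 to 420.

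**The concern.** A look-back tied to the previous survey is harmless only if the surveys are evenly spaced. On the text schedule they are not, because the last interval is twice as long as the others. A patient whose behaviour never changes then has twice the time in which to report an attempt at month 12.

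All patients receive the intervention (section 9.1), so no control arm shares the artifact. The longer window opens at month 6, when the third outreach is made, so a measurement effect could be read as a delayed response to repeated outreach. Month 12 is also the Study 3 primary time point, and section 7 tabulates quit attempts beside 7-day abstinence.

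**Working it through.** **1. Survey times (months from enrollment).** Baseline 1 = 0 and baseline 2 = 3; the follow-ups are at 6, 9 and 15 (Synopsis). Section 7.1 equates 12 months post-implementation with about 15 months after the first baseline: 3 + 12 = 15, which reproduces. Two baselines plus three follow-ups make the five assessments in section 9.7.2.

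**2. Look-back at each survey.**

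| Survey | Look-back (months) |
|---|---|
| Baseline 1 | undefined; no earlier survey |
| Baseline 2 | 3 − 0 = 3 |
| Month 3 | 6 − 3 = 3 |
| Month 6 | 9 − 6 = 3 |
| Month 12 | 15 − 9 = 6 |

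Section 4.1.4 counts from a different origin (3, 6, 9 and 15 months after launch) but also ends with 15 − 9 = 6. If the item refers to the last completed survey, a missed month 6 gives 15 − 6 = 9 months at month 12, and a missed month 3 gives 9 − 3 = 6 months at month 6. Missed surveys are expected: the feasibility benchmark for follow-up is 66–74%, or 33–37 of 50.

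**3. Effect on a count.** The documents give no attempt rate or recall figure, so both are assumptions. With a constant mean of m per 3 months and a fraction r of the older 3 months' attempts recalled, the month-12 mean is m + rm, and its ratio to a 3-month survey is 1 + r.
- Full recall: 1 + 1 = 2.0.
- Half of the older attempts forgotten: 1 + 0.5 = 1.5.

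**4. Effect on a yes/no item.** With the same constant rate for every patient and full recall, a 3-month probability p becomes 1 − (1 − p)².

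| p (3 months) | 10% | 20% | 30% | 40% | 50% |
|---|---|---|---|---|---|
| Month 12, no change | 19% | 36% | 51% | 64% | 75% |

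With half recall, 1 − (1 − 0.30)^1.5 = 41%. If patients differ in rate (gamma, shape 1), the probabilities are 1 − 1/(1 + m) and 1 − 1/(1 + 2m). At m = 0.25, 20% becomes 33% rather than 36%; at m = 1.0, 50% becomes 67% rather than 75%. The rise is smaller but in the same direction.

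**5. Illustration only.** Simulation of month 12 against baseline 2, a contrast that section 7 does not name. There is no true change; m is 0.15–0.5, gamma shape is 1, n = 33 (66% of 50) and the test is two-sided at 0.05. Figures are the proportion of trials showing a false increase.

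| Outcome | Full recall | Half recall | Equal windows |
|---|---|---|---|
| Yes/no | 11–26% | 4–9% | 0.6–1.5% |
| Count | 21–65% | 8–27% | 1.9–3.3% |

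The equal-window ranges also cover n = 50.

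**6. Would an offset for window length repair it?** Dividing by the window gives 2.0/2 = 1.0 with full recall but 1.5/2 = 0.75 with half recall. In the same simulation the latter produced a false decrease in 8–17% of trials at n = 33 and 10–21% at n = 50.

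**7. The schedule table.** The last gap is 390 − 300 = 90 or 420 − 330 = 90 days, with extremes of 390 − 330 = 60 and 420 − 300 = 120. On those days the window would not double. But the month-12 column does not fit its own label: from baseline 2 (days 90–180) it falls 390 − 180 = 210 to 420 − 90 = 330 days later. In the same table baseline 2 can follow baseline 1 (days 0–60) by 90 − 60 = 30 to 180 − 0 = 180 days, so the table does not fix the shorter windows either.

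**The case against.** The strongest objection is that the look-back is attached only to a yes/no question. The count is named in sections 6.2 and 7 without any look-back, and the questionnaire is not in the documents, so a fixed period for the count cannot be excluded. This stands. The doubling of the count holds only if the count uses the same window as the stated item. The yes/no item is affected in any case, in the same direction but less strongly.

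Second, no month-12 versus baseline test is planned. Section 7 summarizes the outcome, explores adjusted effects, and says similar models can be used for secondary outcomes over months 3, 6 and 12. This also stands. A reader might infer that the trial has a false-positive rate as high as the simulated figures, but the documents do not support that: the contrast, rates and recall are all assumed. Nor does silence about an offset, in a plan this general, show that unadjusted counts will be modelled. The tabulation, however, is explicit, and it has no common window.

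Third, this is a secondary outcome in a 50-patient pilot. That is correct. Section 7.1 sets the timing of the primary endpoint and does not make quit attempts primary. Even so, preliminary effectiveness is a stated Study 3 aim (section 4.1).

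Fourth, the table's 90-day gap would largely remove the problem. It would, but the table conflicts with the Synopsis and sections 4.2.3, 6.2 and 7.1.

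**Conclusion.** The point holds on the text schedule. Followed as written, the plan gives a month-12 quit-attempt figure that is not comparable with those at baseline 2, month 3 or month 6, and an unchanged rate would tend to appear as a late rise. With a constant rate, the expected count ratio is 2.0 with full recall and 1.5 if half of the older attempts are forgotten, provided the count shares the stated item's window. For the yes/no form, 30% becomes 51% under full recall and equal rates across patients.

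Three wider readings are not supported:
- Bias in the main effectiveness result: CO-confirmed 7-day abstinence does not use this window.
- Bias in the month-12 analyses of counseling use, medication use or SSL dose: patients who completed month 6 share the same window, so the doubling does not distort comparisons among them.
- An upward bias against baseline 1: that look-back is undefined, so the direction is unknown.

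This should be corrected, but it does not threaten the study's main conclusions. Confidence is medium, because the schedule table and the text disagree and the questionnaire is not available.

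**What to change.** 1. At every Study 3 survey, including baseline 1, ask for the number of quit attempts of at least 24 hours in the past 3 months, in identical words. Use that count for the section 7 summaries and models. This settles the yes/no versus number mismatch, defines baseline 1, and keeps windows equal after a missed survey.
2. State which baseline is used for adjustment.
3. Optionally, at month 12 add a separate question on the earlier time back to the last completed survey, reported descriptively.
4. Do not rely on an offset for window length as the main correction, because it over-corrects if older attempts are forgotten. Keep it as a fallback or sensitivity analysis if the existing wording has already been used.
5. Reconcile the last two survey windows in the Study 3 schedule table with the Synopsis and sections 4.2.3 and 7.1.

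The cost is one reworded item, one sentence in section 7 and a corrected table. The downside is that, without the optional question, attempts in months 6–9, just after the third outreach, are not captured. With it, there is one more question at month 12, and the older half still depends on recall.

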### **4.2.2 Study Procedures and visits study 2**

#### **Patients.**

Enrollment. Patients will provide written, or online, informed consent. They will then complete a baseline survey. Following the baseline survey, they will be called and texted for an outreach call, conducted by a smoking cessation case manager, on staff at the community mental health center. If participants prefer, the outreach session can be conducted via secure video visit or in person. At the outreach session, they can elect to enroll in smoking cessation counseling and/or get help from the case manager to reach out to their providers to obtain smoking cessation medication.

Follow-up. Three months post-baseline, patients will complete a follow-up survey online or by phone. Participants reporting abstinence will complete an expired breath CO test either conducted with a portable CO monitor mailed to the participant, a home visit, or an in-person clinic visit. At the end of the study, 5-6 patients will be selected to complete a qualitative interview.

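### The quit-attempt item, as the protocol describes it, is yes/no, but the secondary outcome is the number of quit attempts; the described item cannot give that number

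*Combined protocol and SAP*

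**What the plan says.** Three places bear on this outcome.

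- **Measurement.** Section 6, Patient Assessments, under Abstinence: patients are asked "if they have made an at least 24 hour quit attempt since the last assessment". No other measure in section 6 concerns quit attempts.
- **Outcome definition.** Section 6.2 includes among the secondary patient outcomes "the number of self-reported ≥24 hour quit attempts and reductions in smoking via cigarettes per day". The main patient effectiveness measure there is CO-confirmed 7-day point-prevalence abstinence.
- **Analysis.** Section 7, Quantitative Analysis, summarises "patient cessation outcomes (7-day PPA and number of quit attempts") at baseline and at 3, 6 and 12 months, then turns to exploratory mixed models: "Models allow for flexible distribution of the outcome (binary, count").

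The assessment schedule fixes how many answers each patient can give. In study 2, "Three months post-baseline, patients will complete a follow-up survey online or by phone". In study 3, "Participants will complete additional follow-up surveys at 3, 6, and 12 months following the second baseline survey".

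**The concern.** An item asking whether an attempt was made records one attempt and five attempts identically. If the surveys follow section 6, the outcome named in sections 6.2 and 7 will not exist in the database, and attempts that were not counted at the time cannot be reliably recovered later.

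The outcome is secondary, but section 7 places it beside 7-day abstinence as one of the two cessation outcomes summarised at each time point, and initial effectiveness is part of Aim 3 (section 3). A yes/no answer also saturates: once most patients have tried at least once in an interval, further attempts no longer change the result. In a pilot of 50 patients, that can hide movement a count would show.

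**Working it through.** **Step 1. Set the texts side by side.** The measured quantity is whether at least one attempt occurred since the last assessment (section 6). The reported quantity is the number of attempts (sections 6.2 and 7). The section 6 sentence uses the same construction for smoking in the last 7 and 30 days, which are plainly yes/no items. Where section 6 wants a quantity, as for cigarettes per day, it says so.

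**Step 2. What the described item can yield.**
- Study 2: one follow-up, so the value is 0 or 1.
- Study 3: three follow-ups after the second baseline, so a sum runs from 0 to 3. It counts intervals containing any attempt, not attempts.
- The study 3 intervals are unequal: 3 - 0 = 3, 6 - 3 = 3 and 12 - 6 = 6 months.
- At the first baseline there is no previous assessment, so the recall window is undefined, although section 7 summarises baseline and adjusts for baseline values.

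**Step 3. How far yes/no departs from the count (illustration).** The plan has no figure to reproduce, and it gives no attempt rate. Assume attempts per interval are Poisson with mean m, varied from 0.5 to 4. Then P(any) = 1 - exp(-m), the share of attempts captured is P(any)/m, and a true rate ratio of 1.5 appears as [1 - exp(-1.5m)]/[1 - exp(-m)].

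| m | P(any) | Share captured | Apparent ratio when the true ratio is 1.5 |
|---|---|---|---|
| 0.5 | 0.39 | 79% | 1.34 |
| 1 | 0.63 | 63% | 1.23 |
| 2 | 0.86 | 43% | 1.10 |
| 4 | 0.98 | 25% | 1.02 |

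**Step 4. Power, as a range.** Section 7 treats 66-74% follow-up as feasible. With 50 patients (section 7.2) that is 0.66 × 50 = 33 to 0.74 × 50 = 37 patients, so n = 35 is a reasonable working size, with n = 50 for complete follow-up. Simulated paired pre-post comparison for a doubling of the mean: Wilcoxon signed-rank on counts, exact McNemar on any/none, two-sided 0.05. Where two runs differ, both values are shown.

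| Assumed attempts | n = 35: counts v yes/no | n = 50: counts v yes/no |
|---|---|---|
| Baseline mean 0.25, gamma-Poisson shape 1, shared patient effect | 0.33-0.36 v 0.18-0.19 | 0.49-0.53 v 0.29-0.32 |
| Baseline mean 1, gamma-Poisson shape 1, shared patient effect | 0.88 v 0.30-0.32 | 0.97 v 0.46 |
| Baseline mean 1, independent gamma draws | 0.54 v 0.23 | 0.69 v 0.31 |
| Baseline mean 1, plain Poisson | 0.92 v 0.51 | 0.98 v 0.71 |

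Exact McNemar is conservative. The asymptotic version raises the yes/no power in the second row to 0.40 (n = 35) and 0.56 (n = 50). For a 1.5-fold rise from a mean of 0.25 at n = 35, power is 0.10 against 0.06, so neither measure is informative. Counts did better in every scenario run, but by very different amounts.

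**The case against.** The strongest reply is that section 6 is a short summary of measures, not the questionnaire. The form is not in the documents. The same sentence says loosely that patients will be asked the contemplation ladder, so it is not item wording. Section 6.2 calls the number of attempts self-reported, which suggests that a count was meant to be asked. This stands as a limit: a reader might infer that the outcome cannot be computed from the data actually collected, and the documents do not show that. They show that the only item described does not yield the outcome. If the form already asks how many, section 6 needs one corrected sentence.

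A reader might also infer that the plan commits to fitting a count model to 0/1 data. It does not. Section 7 allows binary and count distributions without assigning one to quit attempts. A count is the natural reading, because 7-day abstinence is the binary outcome of the pair, but the same sentence would permit a binary model. Cigarettes per day, also to be modelled, is another possible count.

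It is fair, too, that this is an exploratory secondary outcome in a single-arm pilot. No feasibility or acceptability threshold depends on it, and the sample-size statement in section 7.2 does not mention it. That limits the consequence but leaves the contradiction in place.

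**Conclusion.** The point holds as an internal contradiction: following the protocol as written would not produce the stated secondary outcome. This rests on the text alone and needs no assumed rate. It does not touch CO-confirmed 7-day abstinence, feasibility or acceptability.

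The statistical cost is not known, because it depends on attempt rates and between-patient variation that the documents do not give. A reader might conclude that a yes/no item loses most of the power. That is true in some assumed cases, such as a doubling from a mean of 1 with a shared patient effect. From a mean of 0.25 both measures are weak at n = 35 and the gap is much smaller. Any power figure should therefore be given as a range with its assumptions. The correction is worth making before the surveys are fielded because it is nearly free then and cannot be made well afterwards.

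**What to change.** **Preferred.** Change the item in section 6 to ask how many times the patient stopped smoking for at least 24 hours because they were trying to quit, over a stated fixed recall period (for example, the past 3 months). Ask it at the study 2 baseline, at both study 3 baselines and at every follow-up. Any/none can be derived from the count, but the count cannot be derived from any/none. With a 3-month window, the 12-month survey would cover only the last half of its 6-month interval, and the plan should say so.

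**Alternative window.** Keep recall since the last assessment at follow-ups, define a window for baseline, and include log interval length as an offset in the count model to handle the 3-, 3- and 6-month intervals.

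**If the yes/no item is kept.** Redefine the outcome in sections 6.2 and 7 as any attempt of at least 24 hours and analyse it as binary. The recall window still has to be defined at baseline and handled for the unequal intervals.

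In either count version, section 7 should name the model for this outcome. The cost is one reworded item and somewhat harder recall for patients, with no added visit.
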